16.0 REFERENCES

1.0 OBJECTIVES

1.1 Primary endpoint: Complete remission (CR) or complete remission with incomplete count recovery (CRi) rate at 24 months.

1.2 Secondary endpoints:

- 1. Progression-free survival (PFS) at 2 years.
- 2. Overall response rate (ORR) at 6, 12 and 24 months, CR/CRi rate at 6 and 12 months.
- 3. Time to best response.
- 4. Time to alternative treatment.
- 5. Overall survival at 5 years.

1.3 Exploratory endpoints:

- 1. Effect of ibrutinib treatment on immune function.
- 2. Effect of ibrutinib on frequency of subclonal driver mutations.
- 3. Incidence of emergence of subclonal resistance mutations (e.g. C481S mutation in *BTK* and mutations in *PLCG2*).

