2.0 HYPOTHESES

- 1. We will see a high overall response rate, of approximately 90%, similar to that seen in first line treatment of CLL.
- 2. We anticipate seeing a higher rate of complete remission than in treatment of first-line CLL, given patients will have a lower disease burden. In the early report of a large, phase III study of ibrutinib in the first line setting, the CR/CRi rate was 4%, but this increased to approximately 16% after 2 years of follow-up (Pharmacyclics, internal data). We would expect the CR/CRi rate to potentially double when we treat patients early in their disease course; thus, we anticipate a complete remission rate at 2 years of approximately 30%.
- 3. We anticipate approximately 10-15% of patients will stop therapy due to toxicity. In the phase III study mentioned above, the treatment discontinuation rate was 9% at a median follow-up of 18 months. We expect that in an early treatment population, the rates of discontinuation may be somewhat higher, as there may be less willingness from patients and physicians to tolerate troublesome side effects.
- 4. We anticipate that ibrutinib will have beneficial effects on immune function, including improvement in immunoglobulin levers, including IgA(1) and T-cell function.
- 5. We anticipate a low rate of development of resistance mutations.

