Resistance mutations developed during ibrutinib therapy in relapsed/refractory patients, particularly those with del(17p) and complex karyotype. It could be postulated that early treatment, when patients have a lower total disease burden, may result in lower incidence of resistance mutations and superior responses.

3.7. Potential advantages of early therapy with ibrutinib.

Ibrutinib therapy may have beneficial effects on immune function, by inhibiting ITK and skewing T cell responses to T_H1-type;(20) Ibrutinib also reduces PD1/PDL1 expression on CLL cells and PD1 expression on T cells(21) and enhances *in vitro* response to viral peptides ([name], [name] and [name], manuscript submitted). Notably, during continued long-term therapy, infections are noted more frequently within the first year of treatment than subsequently.(22) Improvement in IgA levels(1) has also been seen in patients treated with ibrutinib.

At the time of treatment patients with CLL have significant intra-tumor clonal heterogeneity, with multiple sub-clones, notable for different driver mutations. Treatment with cytoreductive therapy, particularly cytotoxic chemotherapy, results in selection of aggressive subclones, such as those with *TP53* mutation;(23) clones containing *TP53* mutation invariably predominate at relapse, even if their initial frequency is low.(24) CLL cells containing chromosomal abnormalities or mutations which confer resistance to conventional cytotoxic chemotherapy (e.g. del(17p)) show similar sensitivity to novel therapies such as ibrutinib, compared to CLL cells lacking these deleterious mutations.(25, 26) However, during long-term therapy, such patients are more likely to develop novel mutations such as the C481S mutation in *BTK* and activating mutations in *PLCG2*, conferring ibrutinib resistance.(26) To the limits of sensitivity of available testing, these mutations do not pre-date ibrutinib therapy and are thus thought to develop during therapy.(25) Early treatment, at a time when the total burden of CLL cells containing deleterious mutations is likely low, presumably will reduce the mathematical likelihood that a subclone containing an ibrutinib resistance mutation will develop.

3.8 Toxicity of the proposed regimen.

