Diarrhea is the most frequently reported non-hematologic AE with ibrutinib monotherapy and combination therapy. Other frequently reported gastrointestinal events include nausea, vomiting, and constipation. These events are rarely severe and are generally managed with supportive therapies including antidiarrheals and antiemetics. Subjects should be monitored carefully for gastrointestinal AEs and cautioned to maintain fluid intake to avoid dehydration. Medical evaluation should be made to rule out other etiologies such as *Clostridium difficile* or other infectious agents. Should symptoms be severe or prolonged follow the protocol dose modification guidelines (see Section 7.1).

Rash

Rash has been commonly reported in subjects treated with either single agent ibrutinib or in combination with chemotherapy. Rash occurred at a higher rate in the ibrutinib arm than in the ofatumumab arm in study 1112. Most rashes were mild to moderate in severity. Isolated cases of severe cutaneous adverse reactions (SCARs), including Stevens-Johnson Syndrome (SJS) have been reported in subjects treated with ibrutinib. Subjects receiving ibrutinib should be observed closely for rashes and treated symptomatically, including interruption of the suspected agent as appropriate. In addition, hypersensitivity-related events erythema, urticarial and angioedema have been reported.

Lymphocytosis

Upon initiation of single agent treatment with ibrutinib, a reversible increase in lymphocyte counts (i.e., ≥50% increase from baseline and an absolute count >5000/µL), often associated with reduction of lymphadenopathy, has been observed in most subjects (66%) with CLL/ small lymphocytic lymphoma (SLL) treated with ibrutinib as single agent. This effect has also been observed in some subjects with MCL (35%) treated with ibrutinib. This observed lymphocytosis is a pharmacodynamic effect and should not be considered progressive disease in the absence of other clinical findings. In both disease types,

lymphocytosis typically occurs during the first month of ibrutinib therapy and typically resolves within a median of 8.0 weeks in subjects with MCL and 14 weeks in subjects with CLL/SLL (range 0.1-104 weeks).

When ibrutinib was administered in combination with BR or with obinutuzumab in subjects with CLL/SLL, lymphocytosis was infrequent (7% with ibrutinib + BR versus 6% with placebo + BR and 7% with ibrutinib + obinutuzumab versus 1% with chlorambucil + obinutuzumab)

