- **14.2** Ibrutinib has been shown to produce synergistic anti-tumor efficacy with PD-L1 antibodies in mouse lymphoma and other tumor models(32) and to down-regulate PD1/PDL1 on CLL cells and PD1 expression on T cells in peripheral blood. However, the effect of ibrutinib treatment on expression of these immune checkpoint molecules in the marrow, where persistent CLL is frequently seen during ibrutinib therapy, has not been systematically explored. We plan to perform serial assessment of PD-L1, PD-L2 and PD1 by flow cytometry on CLL cells and T cells obtained from both blood and marrow.
- **14.3** Serial analysis of cellular and molecular biomarkers in CLL cells that predict resistance as well as persistence of the disease. A significant proportion of patients with progressive disease were identified to have specific point mutations in *BTK* (C481S) or activating mutations in PLC-γ2 and these mutations appear more common in patients with genomic instability such as those with del(17p) and/or complex metaphase karyotype.(25) We will perform targeted serial deep sequencing using next generation sequencing multiplex panels for known CLL-associated mutations pre-treatment; we will serially monitor the allelic frequency of clonal and subclonal mutations identified at baseline, to identify whether treatment with ibrutinib induces changes in the subclonal architecture. These studies will be performed pre-treatment and at 1, 3, 6, 12 and 24 months from peripheral blood in collaboration with [name] and [name] at Peter MacCallum Cancer Center, Melbourne, Australia. Samples will also be obtained at disease progression.

This sequencing will include serial deep sequencing for BTK and PLC-γ2 mutations, to identify small sub-clones emerging at early time points, whether these expand over time and whether their emergence predicts clinical resistance to therapy.

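### Section 14.3 reads subclonal change from allelic frequency in blood with no stated correction for the CLL share of the sample, so a change in that share can mimic or hide a change in subclones

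*Combined protocol and SAP*

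**What the plan says.** Section 1.3 lists as exploratory endpoint 2 "Effect of ibrutinib on frequency of subclonal driver mutations", and as endpoint 3 the incidence of emerging resistance mutations, with BTK and PLCG2 as examples. Section 2.0, item 5 adds: "We anticipate a low rate of development of resistance mutations".

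Section 14.3 has two parts.

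- **Drivers in general.** Sequencing uses "next generation sequencing multiplex panels for known CLL-associated mutations pre-treatment". After that, "we will serially monitor the allelic frequency of clonal and subclonal mutations identified at baseline, to identify whether treatment with ibrutinib induces changes" in subclonal architecture. On source and timing: "These studies will be performed pre-treatment and at 1, 3, 6, 12 and 24 months from peripheral blood". Also: "Samples will also be obtained at disease progression".
- **BTK and PLCG2.** A separate paragraph plans serial deep sequencing of these genes for small emerging subclones, and asks whether they expand and predict clinical resistance. This part is not limited to baseline findings.

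Section 9.0 (item 14) and Section 10.0 (note 16) give the material as circulating tumor DNA (ctDNA) and peripheral blood mononuclear cells (PBMC). No sorting or enrichment of CLL cells is stated. Section 14.3, note 16 and Section 15.0 contain no correction for CLL share or copy number, no sequencing depth or detection limit, and no rule for samples with little CLL. Section 15.0 gives no analysis of the molecular endpoints.

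**The concern.** The question is whether subclones change relative to one another within the CLL population. The stated measure is the mutant share of all DNA at a locus, which also depends on how much of that DNA comes from CLL cells. Treatment is meant to change that second quantity.

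The protocol gives reasons to expect movement both ways. Section 6.7 reports a lymphocyte rise in 66% of CLL/SLL patients on single-agent ibrutinib, where "lymphocytosis typically occurs during the first month of ibrutinib therapy" and resolves at a median of 14 weeks; sequencing samples fall at months 1 and 3. Later, Section 2.0 expects about 90% response and about 30% complete remission at 2 years, and Section 11.0 requires blood lymphocytes below 4 x 10^9/L for complete remission. Section 14.2 notes that CLL often persists in marrow on ibrutinib, so cleared blood does not show that a clone is gone.

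At stake is the reading of endpoint 2: dilution could be reported as loss of a subclone, a rise in CLL share as a gain, and a real expansion could go unseen. For endpoint 3, a negative result from a sample with few CLL cells excludes less than one from a sample rich in them.

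**Working it through.** **Plan's own figures.** Section 14.3 states none. The only design figure, 78% power in Section 15.2, reproduces: 13 or more responders of 50 gives exact one-sided alpha 0.0475 at 16% and power 0.777 at 30%. Nothing below touches it.

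**Formula.** Let f be the fraction of CLL cells with the mutation and s the CLL share of the sampled DNA. For a heterozygous mutation at a diploid locus, allelic frequency = f x s / 2. A clonal mutation has f = 1, so its allelic frequency is s / 2, and the ratio of subclone to clonal marker is (f x s / 2) / (s / 2) = f.

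**Inputs.** The documents give no value of s, f, depth or detection limit. All values below are assumptions for illustration.

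| Case | f | s | Allelic frequency | Clonal marker | Ratio |
|---|---|---|---|---|---|
| Fixed subclone | 30% to 30% | 90% to 20% | 13.5% to 3.0% | 45% to 10% | 0.30 to 0.30 |
| Tripling subclone | 10% to 30% | 90% to 20% | 4.5% to 3.0% | 45% to 10% | 0.10 to 0.30 |
| Tripling subclone | 20% to 60% | 90% to 30% | 9.0% to 9.0% | 45% to 15% | 0.20 to 0.60 |
| Fixed subclone, s rises | 20% to 20% | 60% to 95% | 6.0% to 9.5% | 30% to 47.5% | 0.20 to 0.20 |

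The first row is a 78% fall (1 - 3.0/13.5) with no clonal change. The second shows the wrong direction, the third hides the expansion, and the fourth shows a false gain.

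**Range.** For a fixed subclone the apparent relative change is s2/s1 - 1, whatever f is. From s = 90% it is -44% at 50%, -78% at 20% and -89% at 10%. Upward from 90% the ceiling is 100/90 = 1.11-fold, so a sizeable false gain needs a lower starting share.

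**Sensitivity for BTK/PLCG2.** With an allelic-frequency limit L, the smallest detectable f is 2L / s.

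| s | L = 1% | L = 0.1% |
|---|---|---|
| 90% | 2.2% of CLL cells | 0.22% |
| 20% | 10% | 1% |
| 5% | 40% | 4% |

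Depth matters greatly. With an assumed call rule of at least 5 mutant reads (binomial), a subclone in 5% of CLL cells is detected with probability about 1.00 at s = 90%. At s = 10% the probability is 0.11 at depth 1,000 and 0.99 at depth 5,000. At s = 1% it is 0.00 and 0.01.

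**The case against.** The strongest reply is that the text does not say uncorrected values will be read as clonal change. Section 14.3 follows clonal and subclonal mutations together, its opening refers to biomarkers in CLL cells, and its target is subclonal architecture. A competent laboratory could form the ratio to a clonal marker from data already planned. That is fair, and it makes the remedy cheap. But the plan names allelic frequency as the measure and PBMC and ctDNA as the material, and nothing obliges anyone to make the correction.

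Four stronger readings are tempting, and the documents do not support them.

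- *Resistance is missed because only baseline mutations are followed.* The BTK/PLCG2 paragraph of Section 14.3 plans a serial search for emerging subclones. The baseline restriction applies only to other drivers.
- *Low-frequency clones are known to take over, so baseline tracking must fail.* Section 3.7 does say "mutation invariably predominate at relapse, even if their initial frequency is low", but of TP53-mutated clones and in the setting of cytoreductive, particularly cytotoxic, treatment. A low-frequency clone found at baseline is also one that Section 14.3 follows.
- *Falling CLL share will make subclones appear lost, and the endpoint will mostly measure clearance.* Early lymphocytosis acts in the other direction, and Section 6.7 reports counts, not CLL share. With complete remission expected in about 30% and few MRD-negative remissions (Section 5.2), deep clearance may be confined to a minority.
- *The resistance result is biased toward hypothesis 5.* That hypothesis has no threshold or test, and the progression sample, when burden should be higher, works against under-counting. Sensitivity falls only per CLL cell: as a share of all sampled cells, a 1% limit detects 2% mutated cells at any s.

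**Conclusion.** The concern holds for endpoint 2. As written, the measure mixes subclonal composition with the CLL share of the sample, and can show change where there is none, miss an expansion or reverse its direction. The algebra assumes heterozygous mutations at diploid loci. The sizes rest wholly on assumed CLL shares; 13.5% to 3.0% for an unchanged subclone is an illustration, not a forecast.

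For endpoint 3 the point is narrower: in responding patients whose blood has cleared, a negative BTK/PLCG2 result carries less information per CLL cell. Its size cannot be given, because depth, detection limit and CLL share are not stated; the calculations run from negligible to nearly complete loss of detection. The progression sample limits the problem among patients who progress, but not among those still responding.

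Only exploratory endpoints 2 and 3 are affected. The CR/CRi test and the sample size do not change.

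**What to change.** Amend Section 14.3, or an analysis plan for the molecular endpoints, before those data are analysed.

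1. Judge subclonal architecture on the estimated fraction of CLL cells carrying each mutation. By default, use the ratio of its allelic frequency to that of a clonal mutation in the same sample. This cancels the CLL share and works for both PBMC and ctDNA.
2. For PBMC only, where CLL share and copy number are available, allow allelic frequency corrected for both as the alternative. Flow cytometry on cells does not give the tumor fraction of ctDNA, so it cannot correct those samples.
3. For BTK and PLCG2, report each sample's detection limit as a fraction of CLL cells. Set in advance the limit above which a sample without a detected mutation is not informative instead of negative.
4. State that, for other drivers, the results describe mutations present at baseline.

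The ratio needs no new assay where a clonal marker exists; patients without one need the second route. That route costs more: blood for immunologic evaluation is scheduled at baseline, months 3, 6 and 12 and progression, but not at months 1 and 24, and on-treatment FISH is on marrow at 6, 12 and 24 months, so no copy-number result is scheduled at months 1 and 3. The price of the change is wider uncertainty, since a ratio of two small frequencies is less precise, and fewer informative samples in deep responders.

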15.0 STATISTICAL CONSIDERATIONS

- **15.1** This is a phase II single arm study of ibrutinib monotherapy in early stage CLL with a predicted time-to-treatment interval of less than 3 years, according to the MDACC nomogram developed by Wierda et al.(4) The primary objective is to evaluate the CR/CRi rate at two years. A maximum of 50 patients will be enrolled in the study with an estimated accrual rate of 4 patients per month; the accrual duration will be approximately 1 year.
- **15.2** The historical CR/CRi rate for patients who are treated when they have symptomatic disease requiring therapy, in the first line setting is 16% at 2 years (Pharmacyclics, internal data). We expect that early therapy with ibrutinib may increase this CR/CRi rate at two years from 16% to 30%. A sample size of 50 patients achieves 78% power to detect a difference of 14% in the 2-yr complete remission rate (i.e. to double the remission rate) using a one-sided binomial test. The target significance level is 0.05. These results assume that the population proportion under the null hypothesis is 16%.
- **15.3** For the primary analysis, we will calculate the proportion of patients with CR/CRi at 24 months, along with 95% confidence intervals. We will test the observed 2-year rate versus the null hypothesis of a 16% rate using a one-sided exact binomial test.
- 15.4 For secondary analyses, proportions of patients with objective response at 6, 12 and 24 months and CR/CRi at 6 and 12 months will be estimated along with 95% confidence intervals. The Kaplan-Meier method will be applied to estimate the progression free survival (PFS), the time to best response, the time to CR/CRi and time-to-alternative treatment survival curves. We will calculate the median time as well as the 2-year and 5-year survival rate and the corresponding 95% confidence intervals. In addition, we will directly compare the observed PFS time to each patient's individual predicted PFS time.

Protocol Amendments

Any amendments to the Protocol or Informed Consent Form must be sent to Pharmacyclics for review and approval prior to submission to the IRB. Written verification of IRB approval will be obtained before any amendment is implemented.

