11.0 CRITERIA FOR RESPONSE

Response will be assessed according to the 2008 IWCLL criteria.(7) Overall response is defined as a CR or PR. Patients with missing or no response assessment will be classified as non-responders. The full criteria are re-produced below. Please note that PET/CT or MRI can be performed for response assessment in lieu of CT scan, if these were performed for disease staging pre-treatment.

Criteria for Complete Remission (CR):

Requires all the following criteria to be met:

- Peripheral blood lymphocytes (evaluated by blood and differential count) below 4 x 10^9/L (4000/μL)
- Absence of significant lymphadenopathy (lymph nodes >1.5 cm in diameter) by CT (or PET) examination of neck, thorax, abdomen and pelvis
- No hepatomegaly or splenomegaly by physical examination (and CT/PET if assessment was abnormal before therapy or if physical exam is inconclusive)
- Absence of constitutional symptoms
- Blood counts above the following values:
 - Neutrophils more than 1.5 x 10^9/L (1500/μL) without need for exogenous growth factors
 - Platelets more than 100 x 10^9/L (100 000/ μ L) without need for exogenous growth factors

- Hemoglobin more than 110 g/L (11.0 g/dL) without red blood cell transfusion or need for exogenous erythropoietin
- Bone marrow aspirate and biopsy, demonstrating at least normocellular for age, with less than 30% of nucleated cells being lymphocytes. Lymphoid nodules should be absent. If the bone marrow is hypocellular, a repeat determination should be made in 4 weeks or when peripheral blood counts have recovered. Minimal residual disease will be assessed by 4 color flow cytometry from the bone marrow.

Patients who fulfill all the criteria for a CR, but who have a persistent anemia or thrombocytopenia or neutropenia apparently unrelated to CLL but related to drug toxicity are classified as complete remission with incomplete blood count recovery (CRi).

Criteria for Partial Remission (PR).

To meet criteria for PR the patient must have achieved at least one of criteria 1-3, below (if abnormal before therapy), as well as one or more of the features listed in section 4, below.

- 1. A decrease in the number of blood lymphocytes by 50% or more from the value before therapy.
- Reduction in lymphadenopathy as measured by PET/CT) as defined by the following:

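### Kaplan-Meier for time to CR/CRi, time to best response and time to alternative treatment ignores competing events, so these secondary curves overstate cumulative incidence

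*Combined protocol and SAP*

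**What the plan says.** Section 15.4 reads: "The Kaplan-Meier method will be applied to estimate the progression free survival (PFS"), and the same sentence extends the method to "the time to best response, the time to CR/CRi and time-to-alternative treatment survival curves". It continues: "We will calculate the median time as well as the 2-year and 5-year survival rate", with 95% confidence intervals. No section states a censoring rule, a competing-event rule or a cumulative incidence method for these endpoints, and none says whether time to best response covers all patients or responders only.

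The primary analysis is separate. Section 15.3 takes the simple proportion in CR/CRi at 24 months and tests it against 16% with an exact binomial test. Section 11.0 adds: "Patients with missing or no response assessment will be classified as non-responders".

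The documents expect some patients to leave treatment. Section 2.0, item 3, says: "We anticipate approximately 10-15% of patients will stop therapy due to toxicity". Section 3.5 reports 79% still on therapy at a median of 28.5 months in the cited first-line phase III study.

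**The concern.** Kaplan-Meier knows two states, event and censored. It assumes that a censored patient has the same future chance of the event as those still under observation. A patient who has died, progressed or moved to another CLL therapy without CR/CRi does not have that chance for a first CR/CRi on ibrutinib. Censoring these patients shrinks the risk set while later responses still count, so 1-KM rises above the share of patients who actually respond.

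The non-responder rule in Section 11.0 does not cure this. It governs response proportions and does not set the risk set of a time-to-event curve. The same exiting patient would be a non-responder in 15.3 and, implicitly, a possible later responder in 15.4. The report could then carry a 24-month value on the CR/CRi curve that is visibly higher than the incidence in the same 50 patients, in a single-arm trial that readers will set against a fixed 16% benchmark.

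For time to alternative treatment, a patient who dies without new therapy can never receive it, so death plays the same role there.

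**Working it through.** **Inputs**
- Sample size 50 (15.1: "A maximum of 50 patients will be enrolled in the study").
- Null rate 16%, target 30%, one-sided 0.05, power 78% (15.2).
- CR/CRi can be documented at the marrow examinations at 6, 12 and 24 months (Section 10.0, note 10).
- Exits without CR/CRi: not given. Section 2.0 expects 10-15% to stop for toxicity. Section 3.5 implies 100% − 79% = 21% off therapy for any reason. Neither figure counts exits that preclude response, so the 10-20% used here is an assumption, as is all timing.

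**Step 1: the plan's own figure.** With X binomial on 50 patients, P(X ≥ 13 | 0.16) = 0.0475 and P(X ≥ 13 | 0.30) = 0.777. A cutoff of 12 would give a type I error of 0.093. The stated 78% is reproduced with success at 13/50 (26%). It depends only on the count of responders, not on any curve.

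**Step 2: responses at scheduled visits.** Let 15/50 reach a first CR/CRi: 3, 4 and 8 at 6, 12 and 24 months. Exits occur before each visit and are censored. Then 1-KM = 1 − ∏(1 − events/at risk). With exits as competing events, the cumulative incidence is 15/50 = 30.0% in every row.

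| Exits before 6/12/24 months | Share | Kaplan-Meier product | 1-KM |
|---|---|---|---|
| 1/1/3 | 10% | 46/49 × 41/45 × 30/38 = 0.675 | 32.5% |
| 2/2/4 | 16% | 45/48 × 39/43 × 27/35 = 0.656 | 34.4% |
| 2/3/5 | 20% | 45/48 × 38/42 × 25/33 = 0.643 | 35.7% |

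Other response timings move these values:
- Early responses (5/5/5): 32.0% at 10% exits and 34.7% at 20%.
- Very late responses (0/3/12): 33.0% at 10% exits and 36.9% at 20%.

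**Step 3: constant hazards.** Let F = 0.30 be the cumulative incidence of CR/CRi, d the exit share and t = F + d. Then 1-KM = 1 − (1 − t)^(F/t).
- d = 0.10: 1 − 0.60^0.75 = 31.8%
- d = 0.15: 1 − 0.55^0.667 = 32.9%
- d = 0.20: 1 − 0.50^0.60 = 34.0%

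**Step 4: if the true rate is 16% (8/50).** Across the same two approaches, 1-KM is about 17-19% at 10-20% exits.

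**Step 5: alternative treatment.** The same algebra applies with death as the exit, so 1-KM is too high. Because the event is an unwanted one, the error counts against ibrutinib. The documents give no expected rate of death or of new therapy, so no size is attached.

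**The case against.** The strongest reply is that little depends on these curves. CR/CRi at 6, 12 and 24 months is already reported as a proportion with a confidence interval, and time to CR/CRi is not among the secondary endpoints in 1.2; it appears only in 15.4. Censoring of exits is implied by the named method rather than written. A rule that keeps non-responders at risk to a fixed horizon would remove the bias, and a time-to-best-response curve confined to responders would have no such exits. It is also unclear whether the 2-year and 5-year rates are meant for every curve or only for PFS. All of this limits the consequence. It does not make Kaplan-Meier the right estimator, since no such rule is stated.

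Stronger readings are tempting, but the documents do not support them:
- **That the primary result is inflated.** It is not: 15.3 uses a proportion and an exact test. Suppose 12/50 respond (2/3/7) with exits of 2/2/4. The curve reads 1 − (46/48 × 41/44 × 30/37) = 27.6%, above the 26% cutoff, yet the test still fails on 12/50.
- **That the error always favours ibrutinib.** It does so for CR/CRi and goes the other way for alternative treatment.
- **That the overstatement reaches about 8 points.** That needs 24% exits before CR/CRi, more than the 10-15% or 21% in the documents, and those figures may include patients who stopped after responding.
- **That any gap from the primary proportion is a Kaplan-Meier error.** The curve counts a first CR/CRi ever reached, while the primary counts status at 24 months. These can differ under any estimator.
- **That every withdrawal is a competing event.** Stopping drug does not preclude response while assessment continues, and non-informative loss is ordinary censoring.

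One further limit: for patients followed at outside centres, telephone contact ends at progression (Section 5.3). Censoring there could understate later alternative treatment, and a competing-risk estimator does not repair that.

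**Conclusion.** The point holds for the secondary curves in 15.4. With a true 24-month CR/CRi incidence of 30% and 10-20% of patients leaving through death, progression or new therapy without CR/CRi, 1-KM overstates the incidence by about 2-6 points; the latest response pattern tried gives just under 7 at 20% exits. The direction follows from the method whenever such exits are censored before later responses occur. The size rests on assumed exit shares and timing. If some exits are only drug stops with continued assessment, or non-informative losses, the bias is smaller. For alternative treatment the curve overstates the need for new therapy by an amount that the documents do not allow one to calculate. For time to best response the same reasoning applies if all patients are included; no size was calculated. The primary proportion, its test and the 78% power stand.

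**What to change.** In 15.4, replace Kaplan-Meier by cumulative incidence (Aalen-Johansen) for three endpoints:
- Time to CR/CRi and time to best response, with death, progression and start of other CLL therapy as competing events.
- Time to alternative treatment, with death as the competing event.

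State that non-informative loss to follow-up is censored at the last assessment, and that patients who only stop drug stay at risk while response assessment continues. Say which patients enter the time-to-best-response analysis. Keep Kaplan-Meier for PFS and overall survival; the latter is a secondary endpoint in 1.2 but is not named in the 15.4 list. It would also help to note that time to CR/CRi describes first attainment and need not equal the primary 24-month proportion.

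The cost is one or two sentences and standard software, with no change to sample size or the primary analysis. The reported CR/CRi curve becomes slightly less favourable.
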